## 12. STUDY POPULATION

### 12.1. Randomization and Blinding

It is planned that approximately 350 patients who meet the inclusion/exclusion criteria will be enrolled in this study at up to 28 U.S. study sites. Patients will be at least 18 years of age and older, of either gender. Efforts will be made to enroll patients ages matching the target study population.

The study product will be administered in a double-blinded fashion, i.e., the treatment assignment will not be known to the patient, to study personnel, or Sol-Gel and its representatives. Patients will be instructed not to discuss the study product with the study personnel. Patients will be randomly assigned in a 2:1 ratio as follows:

- E-BPO Cream, 5% (S5G4T-1) (234 patients)
- Vehicle Cream (S5G4T-2) (117 patients)

Each patient who signs an informed consent, meets inclusion/exclusion criteria, and successfully completes the screening procedures, will be enrolled in the study. The patient randomization schedule will be a permuted block design stratified by investigational site. Blocks will be composed of 3 treatment assignments in a ratio of 2:1 study product and vehicle, respectively. Complete blocks from the randomization schedule will be allocated to investigational sites as they randomize patients to maintain the randomization ratio of 2:1 study product and vehicle, respectively.

Additionally, the staff involved in data management and statistical evaluation will remain blinded until identification of the per protocol population is finished and a database lock memo is issued.

The randomization schedule and treatment code will not be revealed to the patients, study personnel, Sol-Gel or its representatives until after the database lock, except to the Medical Monitor or Principal Investigator for an emergency. Access to the randomization list will be maintained by and limited to the unblinded Biostatistician and the designated personnel directly responsible for labeling of study materials. The Medical Monitor will not have access to the randomization list, but may determine that unblinding one or all patients may be necessary in the case that the safety of study patients is at risk. In an emergency, the study blind may be broken only if:

- In the opinion of the Medical Monitor and/or the PI, it is in the patient's best interest to do so
- Knowledge of the treatment will alter the clinical management of the patient

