#### **19.6. Adverse Events**

All adverse events occurring during the study will be recorded and classified on the basis of MedDRA terminology. Descriptions of AEs will include the date of onset, the date the AE ended, the severity of the AE, the relationship to study product, the action taken regarding study product usage, the action taken to treat the AE, and the outcome. All reported treatment-emergent AEs (TEAEs) will be summarized by the number of Patients reporting AEs, system organ class, severity, seriousness, and relationship to study product. TEAEs are those AEs with an onset on or after the date of the first study product application.

Adverse events will be summarized by treatment group and severity. Each patient will be counted only once within a system organ class or a preferred term by using the adverse events with the highest severity within each category.

Adverse events will be summarized by treatment group and relationship to study product. Each patient will be counted only once within a system organ class or a preferred term by using the adverse events with the greatest relationship within each category.

Comparisons among treatment groups will be made by tabulating the frequency of patients with one or more AEs (classified into MedDRA terms) during the study. The Fisher's Exact test will be used to compare the proportion of patients in each treatment group who report any adverse event at a significance level of 0.05. The specific system organ classes and preferred terms analyzed will be those that are reported by at least one percent of the patients in any treatment group.

All information pertaining to AEs noted during the study will be listed by patient, detailing verbatim given by the investigator, preferred term, system organ class, start date, stop date, severity, actions taken, and drug relatedness. The AE onset will also be shown relative (in number of days) to the day of initial dose of the randomized study product.

Serious adverse events (SAEs) will be tabulated by patient within treatment groups.

In addition, a list of patients who discontinued from the study and a list of patients who experienced SAEs will also be provided.

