5. STUDY OBJECTIVES

The primary objectives of this pivotal study are:

- To assess the efficacy and safety of S5G4T-1 compared to S5G4T-1 Vehicle when applied once daily for 12 weeks in patients with papulopustular rosacea.

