8. STATISTICAL AND ANALYTICAL PLANS

8.1 General Methodology

All statistical processing will be performed using SAS® version 9.3 or later unless otherwise stated. Statistical significance will be based on two-tailed tests of the null hypothesis resulting in p-values of 0.05 or less. These methods are intended to analyze the results of the study.

The primary method of handling missing efficacy data will be based on estimation using the method of Markov Chain Monte Carlo (MCMC) imputation. This method provides robust estimation when the pattern of missingness is arbitrary. Additionally, the estimation will be done for each treatment group separately so that the pattern of missingness for one group does not influence the estimation of missing data for another group. Groups of complete datasets following the estimation will be concatenated to form analysis datasets for the comparative analyses and subsequent imputation result inference with SAS PROC MIANALYZE.

Descriptive statistics will also be derived from the multiply imputed datasets.

Additionally, a model-based multiple imputation process will be used as a sensitivity analysis to the MCMC imputation. Finally, the absolute change in lesion count will be analyzed using a repeated measures analysis of covariance (ANCOVA) for lesion count data and a repeated measures logistic regression model (generalized estimating equations) for the dichotomized IGA.

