8.8.2 Adverse Events (AEs)

All AEs occurring during the study will be recorded and classified on the basis of MedDRA terminology. Descriptions of AEs will include the date of onset, the date the AE ended, the severity of the AE, the relationship to study product, the action taken regarding study product usage, the action taken to treat the AE, and the outcome. All reported treatment-emergent AEs (TEAEs) will be summarized by the number of patients reporting AEs, system organ class, severity, seriousness, and relationship to study product. TEAEs are those AEs with an onset on or after the date of the first study product application; if the AE is not indicated as prior to first application on the CRF then it will be considered a TEAE.

AEs will be summarized by treatment group and severity. Each patient will be counted only once within a system organ class or a preferred term by using the AEs with the highest severity within each category.

AEs will be summarized by treatment group and relationship to study product. Each patient will be counted only once within a system organ class or a preferred term by using the AEs with the greatest relationship within each category.

If relationship to study drug is reported as definitely, probably, or possible, then this is defined as related. If relationship to study drug is reported as unlikely or not related, then this is defined as unrelated.

Comparisons among treatment groups will be made by tabulating the frequency of patients with one or more AEs (classified into MedDRA terms) during the study. The Fisher's Exact test will be used to compare the proportion of patients in each treatment group who report any AE at a

significance level of 0.05. The specific system organ classes and preferred terms analyzed will be those that are reported by at least one percent of the patients in any treatment group.

All information pertaining to AEs noted during the study will be listed by patient, detailing verbatim given by the investigator, preferred term, system organ class, start date, stop date, severity, actions taken, and drug relatedness. The AE onset will also be shown relative (in number of days) to the day of initial application of the randomized study product.

Serious adverse events (SAEs) will be tabulated by patient within treatment groups.

In addition, a list of patients who discontinued from the study and a list of patients who experienced SAEs will also be provided.

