9. DETERMINATION OF SAMPLE SIZE

The following power calculations are based on the observed Week 12 results of the Phase 2 study, SGT-EBP01-09. This study was a three-arm trial including E-BPO cream, 1% and 5%, and vehicle in the treatment of rosacea. Estimates from the E-BPO cream, 5% arm were used in the power assessments. The anticipated randomization ratio is 2:1 for E-BPO cream, 5% and vehicle, respectively. The computations were performed with nQuery Advisor Version 7.0 using a two-sided test with a statistical significance value of 0.05.

A sample size of 86 in the E-BPO cream, 5% and 43 in the vehicle group has 95% power to detect a statistically significant difference in the proportion of patients who have at least a 2-grade reduction at Week 12 from Baseline in IGA and are clear or almost clear. The estimated percentages with a 2-grade reduction at Week 12 from Baseline in the IGA and clear or almost clear are 53.3% and 20.0% for the E-BPO cream and vehicle, respectively.

A sample size of 200 in the E-BPO cream, 5% and 100 in the vehicle group has 95% power to detect a statistically significant difference in inflammatory lesions. The estimated absolute change from Baseline in treatment means were -14.1 and -7.4 for E-BPO cream and vehicle, respectively, with a standard deviation (SD) of 6.70 and 17.24, respectively.

The sample sizes above will be increased to give a planned enrollment of 234 in the E-BPO cream, 5% group and 117 in the vehicle group since the Phase 3 trial is expected to enroll patients who are as a group more severe than those of the Phase 2 trial. This is a consequence of some changes in the inclusion criteria.

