Note: Treatment-emergent adverse events are those events that were not indicated as occurring prior to first application.
Related defined as “Definitely”, “Probably”, or “Possible”. Not Related defined as “Unlikely” or “Not related”.

SOURCE: USERNAME/SPONSOR/PROJECT/JOBNAME (DATE, TIME)

Table 14.3.1.2.2: Summary of Treatment-Emergent Adverse Events by MedDRA System Organ Class and Preferred Term
(Safety Population)
(Page 1 of x)

System Organ Class ^a Preferred Term	E-BPO 5% Cream (N=xxx)	Vehicle Cream (N=xxx)	P-Value ^b
XXXXXXXXXXXXXXXXXXXXXXXXXXXX	xx (xx.x%)	xx (xx.x%)	x.xxx
XXXXXXXXXXXXXXXXXXXXXXXXXXXX	xx (xx.x%)	xx (xx.x%)	x.xxx

^a Counts reflect numbers of subjects reporting one or more adverse events that map to MedDRA. At each level of summarization (System Organ Class or Preferred Term) subjects are counted once.

^b P-value for the difference between treatment groups from a Fisher’s Exact test. The specific system organ classes and preferred terms analyzed will be those that are reported by at least one percent of the patients in any treatment group.

Note: MedDRA Version 21.0

Treatment-emergent adverse events are those events that were not indicated as occurring prior to first application.

SOURCE: USERNAME\SPONSOR\PROJECT\JOBNAME (DATE, TIME)

Table 14.3.1.2.3: Summary of Treatment-Emergent Adverse Events by Severity
(Safety Population)
(Page 1 of x)

System Organ Class ^a Preferred Term	Severity	E-BPO 5% Cream (N=xxx)	Vehicle Cream (N=xxx)
XXXXXXXXXXXXXXXXXXXXXXXXXXXX	Severe	xx (xx.x%)	xx (xx.x%)
	Moderate	xx (xx.x%)	xx (xx.x%)
	Mild	xx (xx.x%)	xx (xx.x%)
XXXXXXXXXXXXXXXXXXXXXXXXXXXX	Severe	xx (xx.x%)	xx (xx.x%)
	Moderate	xx (xx.x%)	xx (xx.x%)
	Mild	xx (xx.x%)	xx (xx.x%)

^a Counts reflect numbers of subjects reporting one or more adverse events that map to MedDRA. At each level of summarization (System Organ Class or Preferred Term) subjects are counted once under the greatest reported severity.

Note: MedDRA Version 21.0.

Treatment-emergent adverse events are those events that were not indicated as occurring prior to first application.

SOURCE: USERNAME\SPONSOR\PROJECT\JOBNAME (DATE, TIME)

Table 14.3.1.2.4: Summary of Treatment-Emergent Adverse Events by Relationship to Study Drug
 (Safety Population)
 (Page 1 of xx)

System Organ Class ^a Preferred Term	Relationship	E-BPO 5% Cream (N=xxx)	Vehicle Cream (N=xxx)
xxxxxxxxxxxxxxxxxxxxxxxxxxxxxxxx	Related	xx (xx.x%)	xx (xx.x%)
	Not Related	xx (xx.x%)	xx (xx.x%)

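### Adverse events are compared inferentially only by Fisher p-values with no risk difference or interval, and at 234 v 117 a non-significant result is uninformative for uncommon harms

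*SAP*

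**What the plan says.** The primary objective pairs efficacy with safety, both against vehicle: "To assess the efficacy and safety of S5G4T-1 compared to S5G4T-1 Vehicle when applied once daily for 12 weeks" (SAP section 5).

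For adverse events, SAP 8.8.2 plans a tabulation by arm plus Fisher's test: "Exact test will be used to compare the proportion of patients in each treatment group who report any AE". Protocol 19.6 has the same rule, with Fisher's test "used to compare the proportion of patients in each treatment group who report any adverse event at a significance level of 0.05". The SAP's general rule makes tests two-sided: "Statistical significance will be based on two-tailed tests of the null hypothesis resulting in p-values of 0.05 or less" (SAP 8.1). System organ classes and preferred terms are tested if at least 1% of patients in either arm report them.

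Two planned shells carry the result, Table 14.3.1.2.2 (TEAEs) and Table 14.3.1.3.2 (serious TEAEs). Each gives n and % per arm and one further column, footnoted "P-value for the difference between treatment groups from a" Fisher's test. Neither has a risk difference or an interval. The shells for overall characteristics (14.3.1.2.1 and 14.3.1.3.1), severity and relationship give n and % without any p-value. Neither document states a power for the adverse event test, an expected adverse event rate, or how a p-value above 0.05 is to be read.

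**The concern.** The safety objective is comparative, so a reader of the safety tables wants to know how large an excess risk on active treatment the data still allow. A p-value does not answer that, and with sparse counts it can be far from 0.05 while a relevant excess remains possible. The sample size was set for the two co-primary efficacy endpoints, so nothing in the plan ensures that the test can detect an uncommon harm.

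This bears on local reactions in particular. Under protocol 16.1 and 16.2, dryness, scaling, itching and burning/stinging count as adverse events only if they lead to treatment interruption, study discontinuation or a new medication. The local reactions that reach these tables are therefore the more consequential ones, and plausibly uncommon.

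**Working it through.** **Inputs.**
- Arm sizes: "planned enrollment of 234 in the E-BPO cream, 5% group and 117 in the vehicle group" (SAP section 9), in line with the 2:1 allocation in protocol 12.1.
- Test: Fisher, two-sided, 0.05 (SAP 8.8.2 and 8.1; protocol 19.6).
- Entry filter: 1% of 234 is 2.34, so 3 active cases; 1% of 117 is 1.17, so 2 vehicle cases.
- Adverse event risks: none in the documents. Those in step 4 are assumptions.

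**1. The plan's own figures.** There is none for adverse events. The efficacy sizes behind the plan do reproduce. For IGA, 53.3% v 20.0% at 95% power with continuity correction gives 86 and 43, as stated. For lesions, -14.1 v -7.4 with SDs 6.70 and 17.24 at 200 and 100 gives about 96% power with unequal variances, against the stated 95%.

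**2. Fisher p-values at 234 v 117.** With k cases in total, the probability that v of them are on vehicle is C(117,v) × C(234,k−v) / C(351,k). The two-sided p sums all tables no more probable than the observed one.

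- 8 active v 0 vehicle: P(v=0) = 0.0375. The tables at v = 6, 7 and 8 are also no more probable: 0.0162, 0.0022 and 0.0001. The sum is p = 0.056.
- 0 active v 3 vehicle: C(117,3)/C(351,3) = 0.0364. No other table is as improbable, so p = 0.036.

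| Active v vehicle cases | Two-sided p |
|---|---|
| 3 v 0 | 0.554 |
| 4 v 0 | 0.306 |
| 5 v 0 | 0.174 |
| 6 v 0 | 0.184 |
| 7 v 0 | 0.100 |
| 8 v 0 | 0.056 |
| 9 v 0 | 0.032 |
| 0 v 2 | 0.110 |
| 0 v 3 | 0.036 |

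So 3 to 8 active cases with none on vehicle pass the filter and are tested, but cannot be flagged. With 1, 2 or 3 vehicle cases, at least 13, 16 or 20 active cases are needed. A smaller safety population changes little: at 200 v 100, 8 v 0 gives 0.0555 and 0 v 3 gives 0.0363.

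**3. What an interval would show.** The Newcombe interval combines the Wilson limits (l, u) of each arm:

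lower = d − √[(p₁−l₁)² + (u₂−p₂)²]; upper = d + √[(u₁−p₁)² + (p₂−l₂)²]

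For 8/234 v 0/117, p₁ = 3.42% (Wilson 1.74% to 6.60%) and p₂ = 0% (Wilson 0% to 3.18%), so d = 3.42 points.
- Lower: 3.42 − √(1.68² + 3.18²) = 3.42 − 3.59 ≈ −0.2.
- Upper: 3.42 + (6.60 − 3.42) = +6.6.

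The planned table would print p = 0.056 where the data allow an excess of up to 6.6 points. For 3 v 0 the interval is −2.0 to +3.7 points, against p = 0.55.

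**4. Power to flag an active-arm excess.** Sum the binomial probabilities over all count pairs with p ≤ 0.05 and a higher observed rate on active.

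| Assumed risk, vehicle v active | Power |
|---|---|
| 1% v 3% | 9% |
| 1% v 5% | 43% |
| 2% v 6% | 34% |
| 5% v 10% | 32% |
| 10% v 20% | 67% |
| 5% v 15% | 82% |
| 10% v 25% | 93% |
| 30% v 50% | 95% |

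**The case against.** The strongest reply is that Fisher is the only test but not the only comparison. Counts and percentages are tabulated by arm, overall and by severity and relationship, and most adverse event shells carry no p-value. A reader can subtract two percentages. Graded local reactions and the patient-rated side-effect question are also tabulated by arm and visit. All of this stands, and it limits the point to a missing estimate and interval.

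A reader might go further and infer that the plan treats p > 0.05 as proof of safety. Nothing in either document says so; both are silent on how the p-values are to be read. Nor does a non-significant result say almost nothing about safety in general: for large differences between common events the power is 82% to 95%.

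A reader might also infer from 8 v 0 (not flagged) and 0 v 3 (flagged) that Fisher's test is biased towards the product and that an interval would cure it. The numbers do not support that. The lopsidedness comes from 2:1 allocation with sparse counts. As rates, the thresholds with none in the other arm are 9/234 = 3.8% and 3/117 = 2.6%. With equal true risks of 1%, the test calls vehicle worse in 2.0% of trials and active worse in 0.02%, but at 5% these are 2.2% and 1.6%, and at 20% 2.2% and 2.1%. The Newcombe interval first excludes zero at the same counts: 9 v 0 (+0.2 to +7.2) and 0 v 3 (−7.3 to −0.2), but not 8 v 0 or 0 v 2 (−6.0 to +0.3). An interval makes the asymmetry visible without removing it. Vehicle terms also have an unreachable zone, since 2 of 117 passes the filter but 0 v 2 gives p = 0.11.

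**Conclusion.** The point holds as a gap in reporting. The only inferential comparison of adverse events gives a p-value without an effect estimate or interval. For uncommon harms a non-significant p-value is uninformative, and for moderate differences it is weak evidence: power is 9% to 43% for the first four scenarios in the power table. For large differences the test is adequate.

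The p-values rest on the planned 234 v 117 and barely move for somewhat smaller safety populations. The power figures rest on assumed risks. The point does not invalidate the safety analysis and has no bearing on the co-primary efficacy conclusions. It is a cheap improvement worth making.

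**What to change.** - Add the risk difference (active minus vehicle) with a two-sided 95% confidence interval, Newcombe or Miettinen-Nurminen, to Tables 14.3.1.2.2 and 14.3.1.3.2.
- Give the same for any TEAE and any related TEAE in Table 14.3.1.2.1, where those rows sit.
- Keep the Fisher p-values, labelled as descriptive.
- State in SAP 8.8.2 that p > 0.05 is not read as absence of a difference.
- Record the change in SAP section 10, since protocol 19.6 specifies the Fisher test at 0.05.

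The cost is a few sentences of SAP text, three table shells and slightly more output. No new data or change in conduct is needed. The display will look less reassuring because the intervals are wide, which reflects what the data can support.

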8.8.3 Clinical Laboratory Evaluation

Urine pregnancy test results will be presented in a by-subject listing.

8.8.4 Other Observations Related to Safety

8.8.4.1 Cutaneous Safety Assessments

Descriptive statistics by treatment group and visit will be provided for dryness and scaling.

8.8.4.2 Local Tolerability Assessments

Descriptive statistics by treatment group and visit will be provided for itching and burning/stinging.

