#### 14.5. Patient Reported Outcomes (PRO)

There are six PRO questionnaires to be administered in the study and each is summarized below. Each will be administered to all patients during the designated study visits with instruction from the Study Staff that they be completed:

- Only by the patient without amendment or interpretation of the patient's response by a clinician or anyone else.
- Prior to any other assessments or procedures.

In the event the patient skips any questionnaire items; the Study Staff will ask the patient to complete the form. The PRO questionnaire data will be entered into EDC, and a copy will be placed with the patient source at the site according to the ICH-GCP guideline (4.9.5).

The PAPS (Appendix 2): The PAPS is a 4-item questionnaire that asks patients to assess the severity of their rosacea symptoms (burning, itching, redness, and bumps) in the 24 hours prior to assessment on an 11-point numeric rating scale (NRS) ranging from “0=none” to “10=worst possible symptom”. The questionnaire can be completed in less than one minute and is administered via pen-and-paper at the Baseline visit and site visits at Weeks 2, 4, 8 and 12 (End of Study) or early termination. Items can be scored individually as well as together to form a total score. In the present context, within visit scores from Items 1 (burning), 2 (itching), and 4 (bumps) are summed and averaged to create a total score that will be used to evaluate efficacy hypotheses.

The PAPI (Appendix 3): The PAPI is a 3-item questionnaire that asks patients to assess the papulopustular rosacea related embarrassment, self-consciousness, and frustration in the 7 days prior to assessment on an 11-point NRS ranging from 0 [“not (concept) at all”] to 10 [“extremely (concept)”]. The questionnaire can be completed in less than one minute and is administered via pen-and-paper at the Baseline visit and site visits at Weeks 2, 4, 8 and 12 (End of Study) or early termination. Items can be scored individually as well as together to form a total score.

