## 16.2. Local Tolerability Assessments

The evaluator will assess local application site tolerability by rating the itching and burning/stinging at the Baseline visit and site visits at Weeks 2, 4, 8 and 12 (End of Study) or unscheduled visits. The evaluator will determine the score for each of these variables by asking the patient to grade their experience over the **past 24 hours**. The definitions of grades provided in [Table 5](#) will be applied to these evaluations. The Local Tolerability Assessment evaluations of itching and burning/stinging will be made by the investigator at the time of the visit.

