**Table 5: Local Tolerability Assessment Scale**

Grade	Description
Itching	
0 – None	No itching
1 – Mild	Slight itching, not really bothersome
2 – Moderate	Definite itching that is somewhat bothersome
3 – Severe	Intense itching that may interrupt daily activities and/or sleep
Burning/Stinging	
0 – None	No burning/stinging
1 – Mild	Slight burning/stinging sensation; not really bothersome
2 – Moderate	Definite warm, burning/stinging sensation that is somewhat bothersome
3 – Severe	Hot burning sensation that causes definite discomfort and may interrupt daily activities or sleep

Application site reactions (itching and burning/stinging) are not to be recorded as adverse events unless they result in either:

- The temporary discontinuation of the study product.
- The discontinuation of the patient from the study.
- The use of a new concomitant medication in order to treat this event.

Any other application site reaction not listed above should be recorded as adverse events in the source document and eCRFs.

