5.3 Safety Objective

The safety objectives of this pivotal study are:

- To determine the nature, severity and frequency of the adverse event rate, the Cutaneous Safety Assessment and the Local Tolerability Assessment of S5G4T-1 compared to the vehicle.

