Table 14.3.1.1: Summary of Cutaneous Safety and Tolerability Evaluations
(Safety Population)
(Page 4 of 8)

Scaling	E-BPO 5% Cream (N=xxx)	Vehicle Cream (N=xxx)
Week 8		
n	xx	xx
0 – None	xx (xx.x%)	xx (xx.x%)
1 – Mild	xx (xx.x%)	xx (xx.x%)
2 – Moderate	xx (xx.x%)	xx (xx.x%)
3 – Severe	xx (xx.x%)	xx (xx.x%)
Week 12		
n	xx	xx
0 – None	xx (xx.x%)	xx (xx.x%)
1 – Mild	xx (xx.x%)	xx (xx.x%)
2 – Moderate	xx (xx.x%)	xx (xx.x%)
3 – Severe	xx (xx.x%)	xx (xx.x%)

Note: No imputation of missing data.

SOURCE: USERNAME\SPONSOR\PROJECT\JOBNAME (DATE,TIME)

Table 14.3.1.1: Summary of Cutaneous Safety and Tolerability Evaluations
(Safety Population)
(Page 5 of 8)

Itching	E-BPO 5% Cream (N=xxx)	Vehicle Cream (N=xxx)
Baseline		
n	xx	xx
0 – None	xx (xx.x%)	xx (xx.x%)
1 – Mild	xx (xx.x%)	xx (xx.x%)
2 – Moderate	xx (xx.x%)	xx (xx.x%)
3 – Severe	xx (xx.x%)	xx (xx.x%)
Week 2		
n	xx	xx
0 – None	xx (xx.x%)	xx (xx.x%)
1 – Mild	xx (xx.x%)	xx (xx.x%)
2 – Moderate	xx (xx.x%)	xx (xx.x%)
3 – Severe	xx (xx.x%)	xx (xx.x%)
Week 4		
n	xx	xx
0 – None	xx (xx.x%)	xx (xx.x%)
1 – Mild	xx (xx.x%)	xx (xx.x%)
2 – Moderate	xx (xx.x%)	xx (xx.x%)
3 – Severe	xx (xx.x%)	xx (xx.x%)

Note: No imputation of missing data.

SOURCE: USERNAME\SPONSOR\PROJECT\JOBNAME (DATE,TIME)

Table 14.3.1.1: Summary of Cutaneous Safety and Tolerability Evaluations
(Safety Population)
(Page 6 of 8)

Itching	E-BPO 5% Cream (N=xxx)	Vehicle Cream (N=xxx)
Week 8		
n	xx	xx
0 – None	xx (xx.x%)	xx (xx.x%)
1 – Mild	xx (xx.x%)	xx (xx.x%)
2 – Moderate	xx (xx.x%)	xx (xx.x%)
3 – Severe	xx (xx.x%)	xx (xx.x%)
Week 12		
n	xx	xx
0 – None	xx (xx.x%)	xx (xx.x%)
1 – Mild	xx (xx.x%)	xx (xx.x%)
2 – Moderate	xx (xx.x%)	xx (xx.x%)
3 – Severe	xx (xx.x%)	xx (xx.x%)

Note: No imputation of missing data.

SOURCE: USERNAME\SPONSOR\PROJECT\JOBNAME (DATE,TIME)

Table 14.3.1.1: Summary of Cutaneous Safety and Tolerability Evaluations
(Safety Population)
(Page 7 of 8)

Burning/Stinging	E-BPO 5% Cream (N=xxx)	Vehicle Cream (N=xxx)
Baseline		
n	xx	xx
0 – None	xx (xx.x%)	xx (xx.x%)
1 – Mild	xx (xx.x%)	xx (xx.x%)
2 – Moderate	xx (xx.x%)	xx (xx.x%)
3 – Severe	xx (xx.x%)	xx (xx.x%)
Week 2		
n	xx	xx
0 – None	xx (xx.x%)	xx (xx.x%)
1 – Mild	xx (xx.x%)	xx (xx.x%)
2 – Moderate	xx (xx.x%)	xx (xx.x%)
3 – Severe	xx (xx.x%)	xx (xx.x%)
Week 4		
n	xx	xx
0 – None	xx (xx.x%)	xx (xx.x%)
1 – Mild	xx (xx.x%)	xx (xx.x%)
2 – Moderate	xx (xx.x%)	xx (xx.x%)
3 – Severe	xx (xx.x%)	xx (xx.x%)

Note: No imputation of missing data.

SOURCE: USERNAME\SPONSOR\PROJECT\JOBNAME (DATE,TIME)

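### The tolerability table has no within-patient comparison with Baseline, so greater relief of disease itching and burning on active could partly mask new irritation

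*SAP*

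**What the plan says.** The safety objective in SAP 5.3 is "To determine the nature, severity and frequency of the adverse event rate, the Cutaneous Safety Assessment and the Local Tolerability Assessment" of the product compared with vehicle.

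Protocol 16.2 has itching and burning/stinging graded 0 to 3 at Baseline and at Weeks 2, 4, 8 and 12. On how the grade is obtained it says: "The evaluator will determine the score for each of these variables by asking the patient to grade their experience over the" past 24 hours. No cause is recorded. Protocol 14.5 describes the PAPSS as a questionnaire that "asks patients to assess the severity of their rosacea symptoms (burning, itching, redness, and bumps) in the 24 hours prior to assessment", so the same two sensations are also measured as disease. Protocol 12.5 lists them, with dryness and scaling, among the local skin reactions patients should be told to expect.

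Under Table 5 the protocol states: "Application site reactions (itching and burning/stinging) are not to be recorded as adverse events unless they result in either" a temporary stop of the product, discontinuation from the study, or a new concomitant medication. Protocol 16.1 applies the same rule to dryness and scaling.

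For analysis, SAP 8.8.4.2 says: "Descriptive statistics by treatment group and visit will be provided for itching and burning/stinging". SAP 8.8.4.1 says the equivalent for dryness and scaling. The shell, "Table 14.3.1.1: Summary of Cutaneous Safety and Tolerability Evaluations", gives counts and percentages of each grade per arm, with a Baseline block first and then each visit. It has no change, shift, worsening or worst-grade block. SAP 8.1.5 has safety data summarized on observed cases. By contrast, vital signs get change from Baseline and a shift table (SAP 8.8.4.3), and PAPSS burning and itching get change from Baseline (SAP 8.7.4).

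**The concern.** A single grade carries two possible causes, disease and product. In a table of separate distributions, a patient whose disease itch clears offsets a patient whose skin starts to itch from the product. The vehicle arm corrects for this only if disease symptoms resolve equally often in both arms. The sponsor plans to test whether PAPSS burning and itching improve differently between arms, so unequal resolution in favor of active is a possibility the plan itself entertains.

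At stake is how well the trial answers its tolerability objective. Reactions that do not lead to interruption, discontinuation or new medication are not adverse events, so Table 14.3.1.1 is the main summary in which they can appear. Observed-case reporting adds a smaller problem: patients who leave because of irritation drop out of the later visit rows. No primary or secondary efficacy conclusion is affected.

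**Working it through.** The plan states no figure on this point, so there is nothing to reproduce. The check is of the mechanism.

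**Inputs from the documents.** Planned arm sizes are 234 active and 117 vehicle (Protocol 19.1.4).

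**Assumptions (the documents give none of these).**
- b, the proportion with grade 1 or more at Baseline, equal in both arms by randomization: 20%, 40% or 60%.
- r, the proportion of those patients whose symptom has resolved by the visit: 60% active and 30% vehicle, or 50% in both.
- w, new onset among patients with grade 0 at Baseline: 5% on vehicle, so some vehicle patients always worsen.

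**Formula.** The proportion with grade 1 or more at a visit is

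P = b(1 − r) + (1 − b)w.

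Subtracting vehicle (V) from active (A):

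P_A − P_V = (1 − b)(w_A − w_V) − b(r_A − r_V).

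The first term is the difference in new onset, as a share of the whole arm. The second, b(r_A − r_V), is the amount by which the by-visit table understates it.

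**Unequal resolution (60% against 30%).** Onset on active is chosen so that the two arms show the same by-visit percentage, which is full masking.

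| b | Persisting, active (b × 0.4) | Persisting, vehicle (b × 0.7) | New onset, vehicle ((1 − b) × 0.05) | By-visit percentage, both arms | New onset, active | Understatement (b × 0.3) |
|---|---|---|---|---|---|---|
| 20% | 8% | 14% | 4% (5 of 117) | 18% | 10% (23 of 234) | 6 points |
| 40% | 16% | 28% | 3% (4 of 117) | 31% | 15% (35 of 234) | 12 points |
| 60% | 24% | 42% | 2% (2 of 117) | 44% | 20% (47 of 234) | 18 points |

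The by-visit percentage is the vehicle sum (for b = 40%, 28% + 3% = 31%). New onset on active is that percentage less the persisting share (31% − 16% = 15%). A shift table would show 15% against 3% where the planned table shows 31% against 31%.

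The exact tie is a construction. It requires onset on active, among patients unaffected at Baseline, of 10/80 = 12.5%, 15/60 = 25% and 20/40 = 50% in the three rows. The understatement in the last column does not need a tie; it depends only on b and the resolution difference.

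**Equal resolution (50% in both arms).** The understatement is b × 0 = 0. Equal by-visit percentages (14%, 23% and 32% for the three values of b) then mean equal onset of 4%, 3% and 2% in both arms. Nothing is masked.

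The formula counts only moves from grade 0 to grade 1 or more. Increases among patients already affected at Baseline would be additional.

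**The case against.** **Baseline is in the table.** A reader might infer that the grades are tabulated with no reference to Baseline. The shell does not support that: each item opens with a Baseline block per arm, so net movement is visible and a net rise over Baseline or over vehicle would show. Only the within-patient link is missing.

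**Masking is conditional.** It needs appreciable Baseline symptoms, better resolution on active, and real irritation. This stands, and the size above is assumed throughout.

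**Other outputs exist.** PGI-SE asks at each post-Baseline visit how bothered the patient is by side effects of treatment, and it is tabulated per arm (Table 14.3.1.6). Reactions that lead to interruption, discontinuation or new medication are adverse events. PAPSS burning and itching have change from Baseline, and Listing 16.2.7.1 holds every grade. The cover is partial. PGI-SE is one overall item with no Baseline and names no reaction. PAPSS asks about symptoms due to rosacea. A listing does not compare arms.

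**A worsening count does not identify cause.** A patient who goes from grade 2 disease itch to grade 1 product itch is not counted as worsened. Worst grade over several visits also picks up disease flares, which may be more frequent on vehicle if active works. This stands, and it is why the added summary should not become the main tolerability comparison.

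**Dryness and scaling are not PAPSS items.** The two-cause argument therefore rests on itching and burning. For the other two items the case is narrower: the same adverse event rule, the same observed-case display, and no separation of new findings from those present at Baseline.

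**Conclusion.** The gap is real and modest. For four items that belong to the stated safety objective, the SAP plans only separate distributions by visit, although it plans within-patient change for vital signs and for the PAPSS items. For itching and burning/stinging, the comparison with vehicle could understate new irritation on active by the Baseline prevalence times the difference in resolution. Under the assumed rates that is 6 to 18 percentage points, and it is zero when resolution is equal.

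A reader might go further and infer that the plan conceals irritation, or that an irritating product would look identical to vehicle while no vehicle patient worsened. The documents do not support either reading. They give no prevalence, resolution or onset rates, several other outputs give partial cover, and zero worsening on vehicle is not a safe assumption: Protocol 7 reports irritation and burning in both groups of an earlier benzoyl peroxide study. The point is an inexpensive improvement to the tolerability display and does not bear on the efficacy conclusions.

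**What to change.** Keep Table 14.3.1.1 as planned. Add to SAP 8.8.4.1 and 8.8.4.2, for dryness, scaling, itching and burning/stinging, one further table per arm in the Safety population with:

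- shifts from Baseline grade to the grade at each visit and to the worst post-Baseline grade;
- the number and percentage of patients worsened by 1 or more grades and by 2 or more grades.

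State how patients without a Baseline grade or without any post-Baseline grade are counted. State also whether unscheduled and early-termination grades enter the worst grade, because SAP 8.1.3 leaves out those taken before Day 8 and those that map to a visit already observed. Using each patient's worst observed grade keeps early leavers in the summary.

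Present the table as an additional comparison with vehicle, with a note that it cannot attribute cause and also captures disease flares. If a numerical example accompanies it, label the rates as assumed, show a range, and let some vehicle patients worsen.

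The cost is one table from data already collected, with no new visits or assessments. The downside is that the tolerability display may look less favorable.
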